approved by the IRB/Partner's HRC and is the most current version. If a new version of the consent form is approved by the IRB/Partner's HRC while a subject is still participating in the study, then the Investigator will inform the subject of the changes and, if the subject agrees to continue study participation, they should sign the updated form.

Electronic informed consent will be obtained prior to performance of any protocol-specific procedures.

c. Subject selection

Ten subjects with one or more hypertrophic scars and ten subjects with scleroderma will be recruited for this study. Each subject will undergo an biopsy of perilesional normal-appearing skin adjacent to lesion to be treated (scar or scleroderma) and an optional biopsy of the treated side at their final visit. Biopsies will only be optional for scleroderma subjects.

IV. Study Procedures

a. Study Visits and Procedures

Baseline Assessment (Phone Call/In-Person Visit)

The baseline/consent assessment will be done in-person or phone call upon physicians discretion. At the baseline visit, eligibility criteria, including a review of medical history and medications, and detailed information about the study will be reviewed. Informed consent will be obtained, if the subject desires to proceed with the study.

Trial treatment Visit 1

Once consented, range of motion assessment (non-facial scleroderma), Mouth Handicap in Systemic Sclerosis scale (facial scleroderma) and Modified Vancouver Scar Scale (hypertrophic scars)(Appendix 2) will be used to assess lesions. Medical photography of the lesions and urine pregnancy test (for female subjects of childbearing potential) will be obtained prior to treatment. OCT imaging and three-dimensional imaging (Cherry Imaging) may also be performed on select consented subjects. The subject will be questioned about itch and pain in the area that will be treated.

Two 3 mm-punch biopsies will be obtained, one from perilesional normal-appearing skin adjacent to treated lesion (scar or scleroderma), and one from skin treated with laser. Biopsies will be optional for scleroderma subjects.

The subject will be anesthetized with 23% lidocaine, 7% tetracaine topical numbing for 30 minutes to one hour, which is standard of care in laser clinic.

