The subject will be anesthetized with 23% lidocaine, 7% tetracaine topical numbing for 30 minutes to one hour, which is standard of care in laser clinic. Once the subject has been anesthetized, they will undergo laser treatment. The entire lesion will be treated with Ultrapulse CO₂ laser DeepFX, an energy 20 mJ-50 mJ and 5%-10% density, 1-2 passes. The area to be treated will not exceed 20cm. Vaseline will be applied evenly with a gloved hand on the entire lesion following the procedure.

Post-procedural visit (final visit, 1 month after treatment visit 3)

One-month after the last treatment The subject will be questioned about itch and pain in the treated area. Range of motion assessment (non-facial scleroderma),

Mouth Handicap in Systemic Sclerosis scale (facial scleroderma) and Modified Vancouver Scar Scale (hypertrophic scars) (Appendix 2) will be used to assess lesions. Lesion marked with surgical marker. Additional medical photography and two 3 mm-punch biopsies will be obtained, one from perilesional normal-appearing skin adjacent to treated lesion (scar or scleroderma), and one from lesional skin treated with laser. Biopsies are optional for scleroderma subjects only. OCT imaging and three-dimensional imaging (Cherry Imaging) may also be performed on select subjects.

Clinical assessment

Clinical photographs taken pre-treatment and post-treatment will be compiled and reviewed in blinded fashion by at least one dermatologist using the Physician's Global Assessment, a widely used scale from the existing literature to determine clinical change from baseline. We will use the Mouth Handicap in Systemic Sclerosis¹ scale for assessing facial scleroderma. For non-facial scleroderma, we will evaluate range of motion of the joint by assessing flexion, extension, supination, and pronation using a goniometer². All scars, facial and non-facial, will be assessed using the Modified Vancouver Scar Scale³.

Cherry Imaging Photography

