We will be using an approved, outside vendor (Forte Research) to make these payments via a reloadable credit card-based system, called Forte Payments. This secure system is similar to a gift card or credit card. If subjects are paid by this system, they will be given a Forte Payments Via card (which is just like a debit card) when subjects enroll in the study. Once the card is activated, the study team will add a payment after each paid visit completed by the subjects. The payment should be available within one (1) business day. Research staff will not know where subjects spend the money. Subjects may use the card anywhere Visa cards are accepted, such as at a grocery store.

We will need to collect subjects' Social Security number in order to make these payments, and it will be shared securely with the company that runs the card-based system. Payments like this are considered taxable income. If subjects receive more than \$600, the payment will be reported to the IRS as income by the hospital.

VII. Biostatistical Analysis

In order to detect a difference of one point assuming a standard deviation of one point on the primary clinical outcome measure, Physician's Global Assessment of Clinical Condition (PGA) scale (a numerical scale from 0-6), a sample size of 10 subjects per condition (10 for scars, 10 for scleroderma, 20 total) is required to achieve a power of 0.8. A student's t test, one sample, two-sided, will be used to determine if any significant statistical difference is present between the clinical response of each treatment arm using the absolute difference between the pre- and post-treatment PGA. A p-value of less than 0.05 is considered statistically significant.

VIII. Risks and Discomforts

There is a potential risk of loss of privacy. We will protect privacy by labeling samples and information only with a code, and keeping the key to the code in a password protected database.

Potential risks of the skin punch biopsy include allergic reaction to the anesthetic, bleeding, infection, poor wound healing, pain, hyper or hypopigmentation and scarring.

Possible risks of fractional laser surgery include pain, scarring, infection, abnormal wound healing, hyper or hypopigmentation.

Possible side effects of topical 23% lidocaine, 7% tetracaine include redness, mild burning sensation, tingling, itching or swelling. Rare side effects include an allergic reaction, which may manifest as dizziness or drowsiness.

IX. Potential Benefits

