4	Slight Improvement	Some improvement ($\geq 25\%$ to $< 50\%$); significant evidence of disease remains
5	No Change	Disease has not changed from baseline (+ or - $< 25\%$)
6	Worse	Disease is worse than at baseline by $\geq 25\%$ or more

prospective cohort study assessing 2-year treatment effect durability. *BMJ Open* 2017;7:e012943.

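### The PGA reading is called blinded, but nothing says what is masked, and a change-from-baseline scale and the listed photograph steps both point the reader to the time order

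*Combined protocol and SAP*

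**What the plan says.** **Reading.** Under Clinical assessment in Study Procedures, the photographs "will be compiled and reviewed in blinded fashion by at least one dermatologist", using the PGA to judge change since baseline. The section does not say what is masked, how image order is concealed, or whether the reader took part in treatment.

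**Scale.** The PGA in Appendix 1 runs from 0 (complete clearance) through 5 (no change) to 6, whose anchor begins "Disease is worse than at baseline". Scores 1 to 4 are bands of percentage improvement. No anchor describes severity at a single time.

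**Photographs.** At Visit 1, "Medical photography of the lesions and urine pregnancy test (for female subjects of childbearing potential) will be obtained prior to treatment"; no marking step is listed there. At Visits 2 and 3 the area is marked so that the same area is treated. At the final visit the text reads "Lesion marked with surgical marker. Additional medical photography and two 3 mm-punch biopsies will be obtained". Visit 1 also lists two punch biopsies after the photographs, one of them in the lesion; they are optional for scleroderma.

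**Analysis.** The Biostatistical Analysis section plans "In order to detect a difference of one point assuming a standard deviation of one point on the primary clinical outcome measure", the PGA, and says that 10 subjects per condition "is required to achieve a power of 0.8". A "t test, one sample, two-sided, will be used to determine" significance, on the difference between a PGA before and a PGA after treatment. The Study design describes two cohorts of 10. No untreated or sham comparison is described.

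**The concern.** Each condition is one treated group compared with its own baseline. The main threat to a photograph score in that setting is a reader who expects benefit, knows which image is later and leans towards it. Masking of time order guards against this. Masking of identity, condition or laser settings does not.

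Two features of the plan work against order masking. The form asks how the lesion has changed since baseline, which presumes that the baseline image is known. And if the listed steps are followed in sequence, ink would appear in one image of the pair and not in the other. In biopsied lesions a healed punch site may be a further cue.

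At stake is the meaning of the only planned test. A significant result could come from the laser, from the reader or from both, and nothing in the design would tell them apart.

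**Working it through.** **1. The plan's own figure.** Inputs from the Biostatistical Analysis section: difference 1, SD 1, two-sided 0.05, one-sample t test. Exact power uses the noncentral t distribution with n − 1 degrees of freedom and noncentrality (1/1)√n. For n = 9 the power is 0.748. For n = 10 (noncentrality 3.162) it is 0.803. The stated 10 per condition reproduces, and this point does not change it.

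**2. Can the form be filled in without the order?** Suppose two photographs differ by 25 to 50%. If the later one is better, the score is 4; if the earlier one is better, it is 6. The images are the same in both cases, and only the order decides. Direct scoring therefore needs the order. An order-masked reader can still say which image is better and by how much, and the score can be assigned afterwards.

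**3. Does the order show in the images?** Visit 1 lists photography with no marking step. The final visit lists marking immediately before photography. This is evidence from the order of sentences, not a stated sequence.

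**4. Illustration of size.** Everything in this step except n = 10 and the 0.05 level is an assumption. No true change exists. An unchanged pair is scored 4 with probability p, 6 with probability q = 0.05, and 5 otherwise. The test is against 5 (no change). Let a be the number of pairs scored 4 and b the number scored 6. Then:

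- mean improvement = (a − b)/10
- s² = [(a + b) − (a − b)²/10]/9
- t = mean/(s/√10), with critical value 2.262 on 9 degrees of freedom

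The outcomes that give significant improvement are:

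- b = 0 and a ≥ 4. At a = 4, the mean is 0.4, s is 0.516 and t is 2.45. (All ten pairs scored 4 has zero variance and is counted as significant.)
- b = 1 and a ≥ 7. At a = 7, t is 2.71; at a = 6, t is 2.24, which falls short.
- None with b ≥ 2. The best case, a = 8 and b = 2, gives t = 2.25.

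Summing the multinomial probabilities over these outcomes gives the third column. The last two columns use the same total error, p + 0.05, divided equally between 4 and 6.

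| p (scored 4) | mean shift, p − 0.05 | false improvement | even split, each way | false improvement |
|---|---|---|---|---|
| 10% | 0.05 | 0.9% | 7.5% | 0.3% |
| 15% | 0.10 | 3.5% | 10% | 0.6% |
| 20% | 0.15 | 8.4% | 12.5% | 1.1% |
| 30% | 0.25 | 23.7% | 17.5% | 2.1% |
| 40% | 0.35 | 41.1% | 22.5% | 2.6% |

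The nominal rate in this direction is 2.5%.

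**5. A second model.** Take normally distributed scores with SD 1, n = 10, no true effect and a constant reader shift. The probability of a significant two-sided result is 0.05 with no shift, 0.11 at 0.25 point, 0.29 at 0.5 and 0.80 at 1.0. At 0.5 point it runs from 0.47 (SD 0.75) to 0.21 (SD 1.25). A shift of one point equals the whole planned effect.

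**The case against.** A reader might infer that the review is simply unblinded. The documents do not show that: they claim blinding and leave the term undefined. Nor is time order the only thing that can be masked. Identity, the in-person scar, motion and mouth-handicap results, symptom reports and laser settings could be too. None of these stops a reader who knows the order from favouring the later image, so the gap stays open.

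A reader might also infer that the PGA rules out order masking. It does not. Paired reading with later mapping works; the plan just does not describe it. The analysis text, which refers to a PGA before and after treatment, could suggest separate scoring of each image, and that could be masked. But the supplied scale has no anchors for a single time, so a pre-treatment score is undefined. This is a conflict to reconcile, not an answer.

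That the final photographs certainly show ink is likewise more than the text supports. The marking sentence is a fragment and may serve the biopsies that follow it, and silence at Visit 1 does not prove bare skin there. The punch-site cue is weaker still. Biopsies are optional for scleroderma, the Subject selection text conflicts with the visit text on which biopsies are taken and when, and nothing says that a 3 mm site would be visible.

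Finally, the error rates come from no document, the plan states no reference value for the test, and at 10 to 15% misrating the false-positive rate is near or below nominal. All of this stands, and it limits the size that can be claimed. It does not remove the mismatch between the scale and the stated blinding.

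**Conclusion.** The point holds in this form: blinding is claimed for the primary endpoint without saying what is masked, the supplied scale needs the time order if filled in directly, and the listed photograph steps may reveal it. In an uncontrolled before/after study the one-sample test then cannot separate reader expectation from treatment effect.

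The size is unknown. Under the assumed rates it ranges from negligible, at 10% misrating, to about two false-positive trials in five, at 40%. What matters is the direction of the errors: the same amount of error without a preferred direction stays at about 3% or less. The figures rest on a test against 5, a 5% rate of worse scores and no true change. The sample size is unaffected.

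**What to change.** 1. State that the reader is masked to time order, and say whether the reader took part in treatment.
2. Take the scored photographs at Visit 1 and the final visit under identical conditions, on unmarked skin and before any biopsy.
3. Remove dates, and apply the same crop or mask to both images of a pair. Covering a biopsy site in one image only would itself reveal the order.
4. Show the pairs in random left/right order, with the key held outside the reading team. The reader records which image is better, or no difference within 25%, and the percentage band.
5. Map to the PGA after unmasking: later image better gives 0 to 4 by band, no difference gives 5, earlier image better gives 6. The scale is lopsided. A mistaken 50 to 75% preference moves the score by 2 points one way (5 to 3) and by 1 the other (5 to 6), so even symmetric errors can lean towards improvement. Report a symmetric summary as well, such as the proportions of pairs in which the later and the earlier image were preferred.
6. Reconcile the analysis text's pre-treatment PGA with a scale that defines no such score, and name the value that the test compares against.

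The cost is a fixed photograph sequence and a randomised reading list. No reader, visit or procedure is added. The downside is that the reader judges pairs instead of filling in the PGA form. Order-masked reading removes reader expectation bias but not natural change over time, so the result should still be described as uncontrolled.

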Ablative fractional carbon dioxide (CO₂) lasers are commonly used to improve the appearance of both conditions, either alone or through laser-assisted drug delivery.⁹⁻¹¹ While the mechanism is not completely understood, ablative fractional laser alone may induce MMPs to help remodel and normalize both collagen and elastin.¹¹

In this study, we seek to evaluate the effects of ablative fractional CO₂ laser treatment on the redistribution/regeneration of collagen on the clinical, microscopic, and molecular profiles hypertrophic scars and scleroderma.

Study design

A prospective cohort study of 10 subjects with hypertrophic scars and 10 subjects with scleroderma.

Analysis of Skin Samples

Optional skin samples will be used to test the hypothesis that fractional laser treatment can improve the clinical appearance of scars and scleroderma.

Skin will be sampled using four 3 mm-punch biopsies. Biopsies will be obtained from the treated lesion (1) and perilesional healthy skin (1) during the first and during the post-procedural visit. Skin biopsies will be optional for scleroderma subjects.

Using histopathological analysis, microscopic and immunohistochemical tissue effects between treatment arms will be compared.

The study will take place at MGH's Clinical Unit for Research Trials & Outcomes in Skin (CURTIS) at [name] or Translational Clinical Research Center (TCRC) on the 12th floor of the White Building.

III. Aims

The aims of this study are:

- To determine the efficacy of ablative fractional laser in clinical improvement of hypertrophic scars and scleroderma.

IV. Subject selection

Subjects will be screened to determine if they meet all the eligibility criteria specified below.

a. Inclusion Criteria

1. Subject must be able and willing to provide written informed consent and comply with the requirements of the study protocol;
2. In good general health, based on answers provided during the screening visit;
3. Any gender and any Fitzpatrick skin type;
4. Age equal to or greater than 18 years old;
5. Subjects in the hypertrophic scar branch must have at least one extragenital hypertrophic scar (defined as abnormal proliferation of scar tissue that forms at the site of cutaneous injury and does not regress and grows beyond the original margins of the scar) at least 4cm in length for scar treatment;
6. Subjects in the scleroderma branch must have eligible extragenital lesions; large enough to treat;

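### Section VII names a one-sample test but states a between-arm purpose that the design cannot serve, and applies it to a pre/post PGA difference that Appendix 1 does not define

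*Combined protocol and SAP*

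**What the plan says.** Section VII is the whole statistical plan. It takes the PGA, scored 0 to 6, as the primary clinical outcome and states that "a sample size of 10 subjects per condition (10 for scars, 10 for scleroderma, 20 total) is required to achieve a power of 0.8". The inputs are a difference of one point and a standard deviation of one point. The test is a Student's t test, described as one-sample and two-sided, at the 0.05 level, on the pre-treatment to post-treatment difference in PGA. The purpose given for that test is to determine whether "any significant statistical difference is present between the clinical response of each treatment arm".

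The design in Section II (Study design) is "A prospective cohort study of 10 subjects with hypertrophic scars and 10 subjects with scleroderma". The only aim in Section III is efficacy of the laser in these conditions. The Study Procedures section gives all subjects the same range of laser settings at three treatment visits and describes no untreated or comparator area.

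Appendix 1 defines the PGA as change from baseline: 0 is completely clear, 5 is no change and 6 is worse. Under Clinical assessment, the PGA is likewise used to judge change from baseline on photographs.

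The histology plan in Section II (Analysis of Skin Samples) says that "microscopic and immunohistochemical tissue effects between treatment arms will be compared". The biopsies listed there are lesional and perilesional skin from the same subject, at the first and the final visit.

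**The concern.** The sentence that defines the primary analysis contradicts itself. Its test is one-sample; its stated purpose is a comparison of arms. The design contains no arms, and its only two groups are two different diseases. Comparing those would not answer whether the laser works in either.

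This matters because no other part of the document says what is being tested. Section VII gives no null value for the one-sample test, so the purpose clause is the only statement of the hypothesis. An analyst could run two within-condition tests, a scar-versus-scleroderma test, or both, and settle the choice after seeing the data. A non-significant comparison of the diseases could then be misread as absence of a laser effect.

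The analysed quantity has a related gap. A scale that scores change from baseline has no pre-treatment value, so a pre/post difference on it cannot be computed as written. Section VII also calls it the absolute difference. If that means the unsigned value, a one-sample t test against zero would not be valid, because unsigned values cannot average to zero unless all are zero.

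**Working it through.** **Inputs, all from Section VII.** Difference 1 PGA point; SD 1 point; two-sided alpha 0.05; n = 10 per condition; stated power 0.8; one-sample t test.

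**Step 1: reproduce the stated power.** For a one-sample t test, df = n − 1 and the noncentrality is (difference/SD) × √n. Power is the probability that a noncentral t variable falls outside ± the 0.975 quantile of central t. With n = 10, df = 9, the noncentrality is 1 × √10 = 3.162 and the critical value is 2.262.

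| Evaluable subjects per condition | Noncentrality | Power |
|---|---|---|
| 10 | 3.162 | 0.803 |
| 9 | 3.000 | 0.748 |
| 8 | 2.828 | 0.681 |

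Ten is the smallest n that reaches 0.8, so the plan's figure reproduces for the one-sample test.

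**Step 2: check for arms.** Section II describes two diagnosis cohorts. The Study Procedures section describes one treatment for both. Section V(a) mentions randomized subjects, but no allocation procedure or second treatment appears anywhere. The purpose clause therefore has nothing to refer to except the two diseases.

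**Step 3: what a comparison of the diseases would give.** For a two-sample t test, df = 2n − 2 and the noncentrality is (difference/SD) × √(n/2). With 10 per group, df = 18, the noncentrality is √5 = 2.236 and the critical value is 2.101.

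- Power for a 1-point difference between conditions: 0.562.
- Power with 16 per group: 0.781; with 17 per group: 0.807. So 17 per group, 34 in all, would be needed for 0.8.
- Difference detectable with power 0.8 at 10 per group: about 1.32 points.

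**Step 4: check the meaning of the SD.** Section VII says only "assuming a standard deviation of one point on the primary clinical outcome measure". Step 1 takes this as the SD of the analysed score. If it were the SD of one of two separate scores with pre/post correlation r, the SD of the difference would be √(2(1 − r)). The documents give no r, so a range is shown.

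| Assumed r | SD of difference | One-sample power, n = 10 | Two-sample power, 10 v 10 |
|---|---|---|---|
| 0 | 1.414 | 0.51 | 0.32 |
| 0.25 | 1.225 | 0.63 | 0.41 |
| 0.5 | 1.000 | 0.80 | 0.56 |
| 0.75 | 0.707 | 0.98 | 0.85 |

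**Step 5: find the null value.** On the Appendix 1 scale, no change is 5. A one-point benefit is then a mean final PGA of 5 − 1 = 4, the slight-improvement category. If the final score is compared with 5, there is one score per subject. No correlation is then needed, and the SD in Step 1 is simply the SD of the final PGA.

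**Step 6: the histology sentence.** With lesional and perilesional samples at two visits from the same subject, the available contrasts are within subject. No between-arm contrast exists here either.

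**The case against.** The strongest reply is that every operational element of Section VII points to a within-condition analysis: the test is one-sample, the quantity is a change, n is given per condition, and the aim is efficacy. On that view the reference to arms is a slip in a purpose clause, and a sensible analyst would test each condition against no change. Most of this stands. The named test and the sample size agree with each other, and a one-sample test could not yield a conclusion about scars versus scleroderma.

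It follows that two stronger readings are not supported. A reader might infer that the study is underpowered at 0.56. That figure belongs to a two-sample test the plan never specifies, and to a 1-point difference between diseases that it never sets as a target. A reader might also multiply the two powers (0.803 × 0.803 = 0.645) and treat the result as the study's chance of success. Nothing in the plan requires both conditions to succeed.

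Loss of subjects is a side issue. Section X(b) lists seven reasons for discontinuation but also provides for final assessments where possible, and no dropout rate is given. The powers for 9 and 8 evaluable subjects are illustrations, not forecasts.

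What the reply does not remove is the gap itself. The correct hypothesis has to be inferred, the null value is nowhere stated, the pre-treatment PGA does not exist, and the reference to arms recurs in the histology plan.

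**Conclusion.** The point holds as a fault in the stated hypothesis and the analysed quantity, not in the sample size. The primary-analysis sentence refers to arms that the design lacks, gives a one-sample test a purpose it cannot serve, and uses a pre-treatment score that the scale does not define. No other section corrects it.

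The stated 10 per condition and power of 0.8 are right for a one-sample test within each condition (0.803). This rests on taking SD 1 as the SD of the analysed score, which the plan does not specify, and on 10 evaluable subjects per condition. The 0.56 is conditional: it applies only if a test of scars against scleroderma was meant, under the same SD assumption. It should not be reported as a power shortfall of this plan.

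The correction should be made before analysis, because this sentence is the only one that fixes the primary hypothesis.

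**What to change.** 1. Replace the test sentence in Section VII with: *For each condition separately, a one-sample two-sided t test compares the mean final PGA with 5 (No Change).* Remove the pre/post difference and the word absolute. This redefines the analysed quantity to fit Appendix 1, so it is more than an edit of one phrase.
2. State that any comparison of scars with scleroderma is descriptive.
3. State that SD 1 refers to the final PGA, and that power is 0.80 per condition with 10 evaluable subjects, with 0.75 for 9 and 0.68 for 8 as illustrations.
4. In the histology paragraph of Section II, replace the comparison between arms with within-subject comparisons, made within each condition, of lesional skin at visit 1 and at the final visit, with perilesional skin as reference.

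The cost is a few sentences in Sections II and VII and no extra subjects. The stated power becomes slightly less favourable if subjects are lost.
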